“Prevention of OUD: The HOME (Housing, Opportunities, Motivation and Engagement) Randomized Trial”

NCT04135703

6/28/2024

Study Protocol

Overview of Design

240 homeless youths between the ages of 18 to 24 years recruited from the streets and drop-in center/shelters will be randomly assigned to 1) 6-months of housing + opioid and related risk prevention services (n = 120), or to 2) opioid and related risk prevention services alone (n = 120). Using an intent to treat design, follow-up assessments will be completed at 3, 6, 9 and 12 months post-baseline. Upon completion of the baseline assessment interview, youths will be randomly assigned to the intervention conditions using a computerized urn randomization program. Four advocates will provide services so that advocate effects can be examined (Baldwin et al., 2011), and each advocate will provide all opioid and related risk prevention services to the youth on their caseload. Advocates will be crossed by condition to “equate” conditions on advocate characteristics.

Sample Inclusion Criteria.

1. Youth were between the ages of 18 to 24 years. Our experience is that landlords will not accept leases signed by youth ages 16-17 years. “Homeless youth” commonly refers to those up to the age of 24 years (Robertson & Toro, 1999; USICH, 2010), thus, this age range generally reflects the age range of the homeless youth population served by providers across the country.
2. Youth met the criteria for homelessness as defined by the federal McKinney-Vento Act (2002) as “lacking a fixed, regular, stable, and adequate nighttime residence” and includes “living in a publicly or privately operated shelter designed to provide temporary living accommodations, or a public or private place not designed for, or ordinarily used as, regular sleeping accommodations for human beings.”
3. Youth failed to meet DSM 5 criteria for Opioid Use Disorder as assessed by the SCID (First et al., 2015).

Screening and intake. Project staff maintain offices within the drop-in center. An RA engaged and screened youth to determine basic eligibility for the study. After the brief screening and stated interest in the project, written consent was obtained and the Structured Clinical Interview for DSM-5 Disorders (SCID) (First, Williams, Karg, & Spitzer, 2015) section on Opioid Use Disorder, was administered to determine formal eligibility.

Project Intervention: Opioid and Related Risk Prevention Services

Housing + Opioid and Related Risk Prevention Services integrates independent housing, Strengths-Based Outreach and Advocacy (SBOA), HIV prevention and MI (Miller & Rollnick, 2012). In the housing + opioid and related risk prevention services condition, youth will be housed in an apartment of their choosing and receive six months of utility and rental assistance of up to \$600 per month. The independent housing is not contingent on the youth’s substance use or attendance in prevention services. SBOA, MI and HIV risk prevention occur simultaneously in this approach. Addressing basic needs but not opioid and other drug use, through MI and service linkage, may lead to difficulty in maintaining basic needs and vice versa. During the intervention, advocates assist youth in accessing community supports so that if more assistance is needed at the end of the intervention period, youth will have been linked to those additional supports. Findings from the pilot study with non-service connected youth indicated that up to 26 advocacy sessions should be offered. Each component of the intervention is described below.

Strengths-Based Outreach and Advocacy (SBOA). Those individuals experiencing homelessness with access to a social service worker, or who utilize community services, are more likely to exit homelessness (Dworsky & Piliavin, 2000; Raleigh-DuRoff, 2004; Zlotnick et al., 2003). In general, the range and severity of adverse outcomes increases over time; the longer a young person experiences homelessness, the more likely they are to experience opioid and other substance use, victimization and mortality, and the harder it becomes to exit street life (Ferguson et al., 2011; Milburn et al., 2006; Scutella et al., 2013), highlighting the importance of engaging disconnected youth to services. SBOA focuses on identifying and engaging youth from the streets and drop-ins/shelters etc. and assisting these youth to meet their basic needs (i.e., referrals to food pantries), obtain government entitlements (i.e., SSDI/SSI, cash assistance, food stamps), and connect to other needed supports (education, job training). The advocates provide referrals and/or transport youth to appointments as needed. The initial meeting provides an opportunity to gather information. The advocate will review each of six general areas with the youth to gather a history and picture of the current situation: (1) housing needs; (2) health care; (3) food; (4) legal issues, (5) employment and (6) education. The advocate will assist youth assigned to the opioid and related risk prevention services only comparison

condition to obtain housing within the community, as is usually provided with SBOA, but unlike the youth in the housing intervention, they are not provided housing by the project. Once this review is complete, an initial intervention plan is developed with specific goals and objectives. Advocates are available 24 hours for crises.

HIV prevention. Some have argued that HIV prevention should be offered to all individuals seeking therapy for drug problems (Roehrich et al., 1994). Every youth will receive the 2-session intervention which uses cognitive-behavioral techniques with a focus on skills building/behaviors (role plays with condom application, cleaning needles, communication/negotiation and problem solving), used in prior projects with homeless youth with success reducing risk behaviors (e.g., Carmona et al., 2014; Slesnick & Kang, 2008). Successful practice of skills is expected to increase confidence and self-efficacy which is expected to increase the youth's use of skills including condom use and negotiation in other micro-system interactions. The first session is devoted to AIDS education, assessment of risk, risk reduction and skills practice. Session 2 focuses on sexual assertiveness and practicing negotiation. Role plays are incorporated to allow the youth to practice social competency skills relevant to their life situations.

Motivational Interviewing (MI). Typically offered as a brief intervention of 1-2 sessions, Motivational Interviewing (MI, Miller & Rollnick, 2012) has a strong record of efficacy in the prevention and treatment of alcohol and other drug use disorders (Copeland et al., 2015; Miller & Rollnick, 2012). MI assumes that the responsibility and capability for change lie within the client and needs to be evoked (rather than created or installed). Baer, Peterson and Wells (2004) provide some rationale for utilizing brief feedback and motivational intervention with street living youth - the intervention is less costly and demands much less of a hard-to-reach population than more intensive interventions. Utilizing a sample of runaway adolescents recruited from a runaway shelter, Slesnick et al. (2013) found that substance use reductions were significant for those assigned to MI even to two years post-treatment. The advocate will administer MI. Four principles guide the practice of MI: express accurate empathy, develop discrepancy, roll with resistance and support self-efficacy. The Project Match manual was adapted for homeless/runaway youth in prior trials in consultation with [name] and [name] (NIAAA grant no. R01AA12173 and NIDA grant R29DA11590). Adaptation of the manual included attention to the unique life situation of homeless youth in understanding motivations and challenges to recovery while homeless. Session 1 begins with a period of open-ended MI, to establish therapeutic rapport and elicit client change talk. In session 2 the advocate continues to focus on enhancing intrinsic motivation for change, developing discrepancy, transitioning as appropriate into the negotiation of a change plan and evoking commitment to the plan.

Housing + Opioid and Related Risk Prevention Services. Those randomized to receive housing + opioid and related risk prevention services will receive all the above and also receive 6-months of rental and utility supports in an apartment of their choosing.

All youth completed a **baseline and follow-up assessment** which included self-report, interview, and physiological measures, with the following outcomes.

Primary Outcomes: **1)** time to OUD (SCID) (UH3) **2)** % days opioid use (Form 90) (UG3, UH3).

Secondary Outcomes: **1)** % days other alcohol/drug use (Form 90), **2)** drug use consequences (SIP) **3)** HIV risk score (0-7) **4)** % days housed (Form 90), **5)** BDI-II depression score, **6)** Physical health score (SF-6), **7)** % days employed and % days in school/training (Form 90), **8)** resilience score (BRS), **9)** coping (task, emotion and avoidance) scores (CISS) **10)** cognitive distortions score (CD-QUEST), and **11)** self-regulation score (SSRS).

Mediators: Primary: **1)** # of service contacts (service log), **2)** working alliance score (WAI), **3)** social support (SNI): number and satisfaction of support persons, and **4)** # of violence/victimization exposures (HEQ).

Secondary: **1)** Stress (2 dv's) self-reported stress score (Cohen's PSS), and physiological hair cortisol level, and **2)** Self-efficacy (3 dv's): HIV, substance use, and perceived personal control scores.

Study Aims were as follows:

Specific Aim 1. Evaluate the relative efficacy of housing + opioid and related risk prevention services compared to prevention services alone (N = 240). Hypothesis. Youth receiving the 6-month housing + prevention services will show better 3, 6, 9 and 12 month outcomes than those receiving prevention services alone. Fewer Housing First youth will progress to OUD and will be more likely to remain housed at one year.

Specific Aim 2. Test the effects of the primary and secondary mediators on the primary outcome (opioid use/time to OUD) and secondary outcomes. Hypothesis. Inasmuch as the intervention triggers

successful social micro and meso-system interactions or social resources (e.g., advocate and social service meetings), individual resources will be activated – e.g., stress will decrease and self-efficacy will increase, leading to multiple positive outcomes.

Specific Aim 3. Explore how moderators affect individual's response to housing + opioid and related risk prevention services.

Statistical Analysis Plan

Missing Data. The patterns of missing data will be first examined before each analysis. If data are missing at random, they will be estimated using full information maximum likelihood (FIML) or multiple imputations (MI) method. When data are missing completely at random (MCAR) or are missing at random (MAR), both FIML and ML produce unbiased results (Enders, 2010). The main statistical program used for this study, MPlus, can handle missing data by providing FIML estimation. If the missingness cannot be explained by observed data, that is, data are Missing Not at Random (MNAR), data analysis will be conducted using the pattern mixture model (Roy, 2003) framework.

Study Aim 1. The impact of the two intervention conditions (i.e., 6-months housing + opioid and related risk preventive services, and opioid and related risk preventive services alone) on the primary and secondary outcomes will be tested in Aim 1. Specifically, the primary outcome, time to the onset of OUD, will be analyzed using the discrete-time survival analysis. In this analysis, whether the onset of OUD has occurred at a specific time point is included as the indicator of a latent factor, the proportional odds for the hazard of OUD, which is predicted by the contrasts between conditions. It is expected that youth assigned to the housing + preventive services condition will have longer delay in the onset of OUD than those in the preventive services alone condition. For the primary outcome, % days opioid use, and secondary outcomes that are continuous variables, latent growth models (LGM) will be conducted to estimate the trajectories of change across five time points (baseline, 3, 6, 9 and 12 months follow-up) to estimate the trajectories of change over time. Differences between treatment conditions on estimated growth parameters, including intercepts (i.e., initial status) and slopes (i.e., the rates of change), will be tested. It is expected that those assigned to the 6-month housing + opioid and related risk prevention services group will show greater decreases in opioid use (for those using opioids), as well as greater improvement in secondary outcomes, and that these improvements will maintain for a longer period of time, compared to those assigned to prevention services alone. To increase validity of the conclusions drawn from the analysis, the number of intervention sessions and contacts with other service providers will be covariates in the LGM analyses.

Study Aim 2. To test the proposed behavioral change mechanisms (i.e., social and individual resources), a series of path analysis will be conducted. Specifically, we will first test whether the primary mediator (e.g., service connections, social support) or secondary mediator (e.g., self-efficacy, stress) assessed at the 3- or 6-month follow-up mediates the association between intervention and outcome at 6-month and 9/12-month follow-up, respectively. We expect that the intervention condition with the housing component will produce greater improvement in social/individual resources, which in turn will predict better outcomes. We will also estimate serial mediation models, in which both primary and secondary mediators are included (Figure 1), to test whether intervention first affects social resources, which then lead to changes in individual resources and subsequent outcomes. In these models, the baseline assessment of the mediators and outcomes will be controlled for in the analysis. Following MacKinnon and colleagues (MacKinnon et al., 2007), the product of the coefficient of the path from the independent variable to the mediator(s) and the coefficient of the path from the mediator(s) to the outcomes will be computed as the indirect (mediation) effect between the intervention and outcomes. The strength and significance of the mediation will be estimated using a bootstrap sampling method (Shrout & Bolger, 2002).

Study Aim 3. The effect of the moderating variables (age, sex, race/ethnicity, sexual orientation, childhood abuse history, and baseline substance use and service connection) will be tested by examining the interaction between intervention type and each moderator in predicting outcome slopes in the growth models and survival analysis. The contrast between intervention conditions will be multiplied by each moderator variable to form an interaction term. Next, the interaction terms will be included in the analyses for Aim 1 for the primary/secondary outcomes, one at a time, and their strength of association with the outcome slope will be assessed while controlling the direct effects of the predictors on outcome and the direct effect of moderator variables on outcome. If the interaction term is significant, this suggests moderation.

Statistical Power Analysis. The power analyses were conducted using the Monte Carlo simulation method. The MPI's ongoing study testing the effect of housing support on homeless mothers reveals medium effect sizes in reducing substance use ($d = .49$) and depressive symptoms ($d = .59$), and a large effect ($d = 1.26$) in improving housing stability, favoring the housing intervention over TAU/assessment only. Given that the proposed study tests housing support against an active intervention, and the differences between the two conditions may be smaller than that between housing support and TAU, we assumed small-to-medium effect sizes when conducting the power analysis. For the latent growth analyses, with dichotomous predictors (contrasts between intervention conditions) that have regression coefficients of .15 (small-to-medium effect size) for the slopes of growth factors (Muthén & Muthén, 2002), a sample size of 240, with an overall attrition rate of 15%, can produce a power of .86 to detect the intervention effect on the growth rate of outcomes. For Aim 2, in the simulated mediation analysis, we again assumed a small-to-medium effect size for the intervention effect. Data from the MPI's ongoing clinical trial shows that the associations between social/individual resources and outcomes are of medium effect size or larger (e.g., personal control is associated with depressive symptoms at $r = -.46$ and with general mental health at $r = .43$). Thus we assumed medium effect sizes for the mediator to outcome pathways. Following the model specification suggested by Thoemmes et al., (2010), the proposed sample size could provide a power of .93 to detect mediating effects for the one mediator model and a power of .82 for the serial mediation model with two mediators.

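### The trial uses four advocates so that advocate effects can be examined, but no planned model contains an advocate term, so that stated purpose has no analysis

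*Combined protocol and SAP*

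**What the plan says.** The Overview of Design gives a reason for the number of advocates: "Four advocates will provide services so that advocate effects can be examined". Each youth is served by one of them, since "each advocate will provide all opioid and related risk prevention services to the youth on their caseload". It then says "Advocates will be crossed by condition" and gives that feature a separate purpose, which is to make the arms alike in advocate characteristics. There are 120 youths per arm.

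The Statistical Analysis Plan sets out its models as follows:

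- **Study Aim 1, time to OUD:** a discrete-time survival model with a latent hazard factor, "which is predicted by the contrasts between conditions".
- **Study Aim 1, % days opioid use and continuous secondary outcomes:** latent growth models with the arm contrast on intercept and slope; "the number of intervention sessions and contacts with other service providers will be covariates in the LGM analyses".
- **Study Aim 2, path models:** "the baseline assessment of the mediators and outcomes will be controlled for in the analysis".
- **Study Aim 3:** interactions of arm with seven youth-level moderators, one at a time.

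The Statistical Power Analysis states a power of .86 for the growth models, with N = 240, 15% attrition and a coefficient of .15 on the slope. It mentions neither an intraclass correlation nor clustering by advocate.

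**The concern.** The protocol gives a reason for having four advocates, and the analysis plan never acts on it. The models list their predictors and advocate is absent from each, so a team following the plan as written would finish without having looked at advocates.

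Two things are at stake. First, differences between advocates that affect both arms alike stay in the residual, although the crossed design would allow them to be removed at almost no cost. Second, nothing in the plan would show whether a housing effect is spread across the four advocates or comes mainly from one of them.

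**Working it through.** **The plan's own figure.** The power of .86 can be neither reproduced nor refuted, because slope variance, residual variance and alpha are not given. A generalised least squares calculation for a slope difference over five equally spaced waves, at an assumed two-sided alpha of .05, was run over assumed slope variances of .05 to .20 and residual variances of .25 to 1.0. Power ran from about .50 to .99. Some settings match: slope variance .08 with residual variance .5 gives .864 with dropout. The figure .86 is therefore taken as given.

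**Inputs.** From the documents: 4 advocates, crossed with arm, and 120 youths per arm. Assumed: equal caseloads, so 120/4 = 30 youths per advocate-by-arm cell; a share ρ of outcome variance due to advocates (.01, .05, .10); and in step 2 a further share ρᵢ for each advocate-by-arm cell.

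**Step 1. Advocates shift both arms equally, linear outcome.** Crossing cancels a shared advocate effect from the arm difference, so the true variance is proportional to 1 − ρ. The unadjusted model still counts advocate variance in the residual.

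- Closed form, many advocates: SE ratio = 1/√(1 − ρ).
- Four advocates: the within-arm sample variance picks up only f = (3/4)(120/119) = 0.756 of ρ, so SE ratio = √[(1 − ρ + 0.756ρ)/(1 − ρ)]. At ρ = .05 this is √(0.9878/0.95) = 1.020. A simulation of 20,000 trials gave the same excesses of 0.4%, 2.0% and 4.1%.
- Power after adding the term = Φ(3.040 × SE ratio − 1.96), where 3.040 = 1.96 + 1.080 and Φ(1.080) = .86.

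| ρ (assumed) | SE excess, closed form | SE excess, four advocates | Power, closed form | Power, four advocates |
|---|---|---|---|---|
| .01 | 0.5% | 0.4% | .863 | .863 |
| .05 | 2.6% | 2.0% | .877 | .873 |
| .10 | 5.4% | 4.1% | .893 | .886 |

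**Step 2. The housing effect differs by advocate, and inference extends beyond these four.** The true variance is now proportional to (1 − ρ − ρᵢ) + 30ρᵢ, and the unadjusted model's variance to (1 − ρ − ρᵢ) + 0.756(ρ + ρᵢ). At ρ = .05 and ρᵢ = .02 these are 0.93 + 0.60 = 1.53 and 0.93 + 0.053 = 0.983, so the ratio of unadjusted to true SE is √(0.983/1.53) = 0.80. By simulation at ρ = .05:

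| ρᵢ (assumed) | Unadjusted SE / true SE | Type I error of a nominal 5% test |
|---|---|---|
| .005 | 0.95 | 6.5% |
| .01 | 0.89 | 8.2% |
| .02 | 0.80 | 11.9% |
| .05 | 0.64 | 21.5% |

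The break-even point is ρᵢ = 0.756ρ/(30 − 0.756), which is .0013 at ρ = .05. Above that share the sign of the error reverses. Adding advocate main effects alone does not repair it: type I error at ρᵢ = .02 is then 12.8%.

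**Step 3. Time to OUD.** A discrete-time logit model was simulated 300 times with four follow-up intervals, an assumed log odds ratio of −0.7 and an assumed advocate standard deviation of 0.6 on the logit scale. Without an advocate term the mean estimate was −0.67, the SE 0.281 and the power .69. With it they were −0.71, 0.285 and .72. Omission did not enlarge the SE; it attenuated the estimate slightly.

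**The case against.** The strongest reply is that the plan promises little here. Saying that effects can be examined describes a capability and does not commit the trial to an analysis; the analysis plan is silent and does not exclude one. That is fair, and it is why this is a gap in specification and not a broken commitment. It does not remove the gap, because the capability was the stated reason for using four advocates and nothing says how it will be used.

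A reader might infer that crossing the advocates is wasted. The documents do not support that: crossing has its own stated purpose, balance between arms, and achieves it without any model term.

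A reader might also infer that the arm comparison is simply conservative. That holds only for an effect shared by both arms, a linear outcome and balanced caseloads. It does not describe the model for time to OUD, the first-listed primary outcome, and it reverses with a small amount of advocate-by-condition variation if inference goes beyond these four. Equally, nothing in the documents shows that such variation exists, so they do not support a claim that type I error is inflated either.

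Two further reservations stand. The stated power concerns a growth slope, so an intraclass correlation for the outcome itself does not carry over exactly. The session and service-contact covariates may also absorb some of the difference between advocates. Both are reasons to read the power gains in step 1 as upper limits.

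**Conclusion.** The point holds as a minor one. The stated purpose of examining advocate effects has no planned analysis; that rests on the text alone and needs no assumption. The statistical consequences are conditional. A shared advocate effect on a linear outcome costs a little precision, at most about 5% of the SE and .03 of power at an intraclass correlation of .10. For time to OUD the consequence is slight attenuation. With advocate-by-condition variation and wider inference, the SE is too small.

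The intraclass correlations, equal caseloads, two-sided 5% level and simulation settings are all assumptions. The documents also do not say how youths are allocated to advocates. Neither the randomised comparison nor any primary conclusion is invalidated.

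**What to change.** In the analysis plan for Study Aim 1:

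1. Add advocate as a fixed factor: three indicators in the survival model, and three on each growth factor tested. Four levels are too few to estimate a random variance well.
2. Define it by the assignment made at entry, so that it cannot depend on later contact.
3. Report the arm difference by advocate (advocate-by-condition) as a descriptive sensitivity check.
4. State that inference is conditional on these four advocates, since main effects alone do not cure the interaction case.

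The cost is three parameters in the survival model and about six per growth model (three on the intercept and three on the slope). The by-advocate differences will be imprecise, with about 30 youths per cell if caseloads are equal. No new data are needed if caseload assignment is on record, as the design implies.

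### The housing outcome is modelled across the rent-paid and post-rent months together, so the plan has no clean test of whether youth remain housed at one year

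*Combined protocol and SAP*

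**What the plan says.** Under Project Intervention, in the housing arm "youth will be housed in an apartment of their choosing and receive six months of utility and rental assistance". That housing carries no conditions: "The independent housing is not contingent on the youth’s substance use or attendance in prevention services". Comparison youth are helped to look for housing in the community, but, as the SBOA section puts it, "unlike the youth in the housing intervention, they are not provided housing by the project".

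Per the Overview of Design, "follow-up assessments will be completed at 3, 6, 9 and 12 months post-baseline", so visits run from baseline and not from move-in.

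% days housed (Form 90) is secondary outcome 4. Specific Aim 1 predicts better outcomes at all four follow-up visits, and then adds a sentence specific to housing: "Fewer Housing First youth will progress to OUD and will be more likely to remain housed at one year".

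The Statistical Analysis Plan (Study Aim 1) puts every continuous secondary outcome into a latent growth model over five time points and compares arms on the intercept and the slope. It does not define a housed day, separate project-paid days from others, or name a contrast for the period after rent support ends.

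**The concern.** For half of follow-up the project buys, in one arm only, the thing the outcome measures. An early difference is then expected almost by construction and says little about what happens once payment stops. The hypothesis is about what happens then.

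A growth model summarised by an intercept and a slope pools the two periods. If housing rises while rent is paid and falls back afterwards, the trajectory is not a straight line, and the fitted line carries part of the paid period into the 12-month value. The trial could report youth as still housed at one year when the arms no longer differ. It could also report a slope against the housing arm when the arms are simply equal again.

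**Working it through.** **Figure to reproduce.** The documents give no effect size or power figure for this outcome in this trial. The only Aim 1 power figure (.86 for a growth-rate coefficient of .15) cannot be rebuilt, because alpha and the slope and residual variances are not stated. Nothing below depends on it.

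**Inputs from the documents.** Rent support lasts 6 months, in one arm. Visits are at 0, 3, 6, 9 and 12 months. Arms are compared on intercepts and slopes.

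**Assumptions.** Growth is linear (the plan names no other shape). Each visit covers the preceding three months. Randomisation gives no baseline difference. Move-in is immediate. Paid nights count as housed. Nothing is retained after rent stops.

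**Share of follow-up that is paid.** 6/12 = 50%: two of four follow-up visits, or two of the five model time points.

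**Linear model.** Code visits t = 0, 1, 2, 3, 4. The true arm differences are y = (0, e, e, 0, 0).

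- *Free intercepts.* Mean t = 2 and mean y = 0.4e. Σ(t-2)y = -e and Σ(t-2)² = 10, so the slope is -0.1e per visit. The intercept is 0.4e + 2(0.1e) = 0.6e. At 12 months: 0.6e - 4(0.1e) = **+0.2e**.
- *Common intercept.* Σty = e + 2e = 3e and Σt² = 30, so the slope is +0.1e per visit. At 12 months: 4(0.1e) = **+0.4e**.

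The true 12-month difference is 0 in both cases.

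**How firm these are.** Both are least-squares fits with equal weights. With complete data, equal residual variance and random intercepts and slopes, the free-intercept result is the same whatever the variance components. The common-intercept result is not. It shrinks as between-youth variance grows and can change sign, and the documents do not give those variances. So +0.4e is an illustration, not a forecast.

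**Size of e (assumed range).** Let comparison youth be housed a fraction c of days, and let the paid apartment fill a fraction u of the days otherwise unhoused: e = u(1-c).

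| u | c | e (points) | 0.2e | 0.4e |
|---|---|---|---|---|
| 0.5 | 0.6 | 20 | 4 | 8 |
| 1.0 | 0.2 | 80 | 16 | 32 |

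**Late move-in (assumed; no delay is given).** Move-in at month 2 means rent to month 8, which covers 2 of the 3 months in the 6-9 month window. The differences become (0, e/3, e, 2e/3, 0). With free intercepts, Σ(t-2)y = -e/3 + 2e/3 = e/3, so the slope is +0.033e. The 12-month value is 0.4e + 2(0.033e) = +0.47e; the truth is still 0. Only a delay beyond three months puts paid nights in the last window. Move-in at month 4 means rent to month 10, or 1 of those 3 months.

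**Does a knot at 6 months cure it?** Two straight lines joined at month 6, fitted to (0, e, e, 0, 0), give (0.2e, 0.6e, e, 0.4e, -0.2e). The residuals (-0.2e, 0.4e, 0, -0.4e, 0.2e) sum to zero. They also sum to zero against t (0.4 - 1.2 + 0.8) and against the second-segment term (-0.4 + 0.4), so this is the least-squares fit. It misses 0 by the same amount in the other direction. If the level may also drop after 6 months, the 9- and 12-month points are fitted exactly and the 12-month value is 0.

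**The case against.** Several stronger readings are tempting, and the documents do not support them.

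- *The outcome must favour the housing arm whichever contrast is used.* It need not. With immediate move-in and free intercepts the slope difference is negative. On the nominal schedule the window before the 12-month visit holds no paid nights, so a contrast there is clean.
- *The one-year hypothesis is itself an artefact.* It refers to a time about six months after nominal rent support ends. The fault is that no analysis isolates it.
- *The trial will report a 12-month average inflated by paid nights.* A simple average over follow-up is not the planned statistic.
- *The early measure is pure delivery.* Youth can decline or leave an apartment, and comparison youth can find one with staff help. Days housed at 3 and 6 months are a legitimate intent-to-treat outcome, and Specific Aim 1 predicts benefit there.
- *Paid nights should be scored as not housed.* That would misclassify youth who are living in an apartment, and in one arm only.

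That paid nights count is itself an inference. Form 90 coding is not described. The eligibility definition of homelessness, "lacking a fixed, regular, stable, and adequate nighttime residence", makes it the natural reading, since a rented apartment would ordinarily fall outside that definition. Lease-up delay is likewise assumed. Finally, this is one of eleven listed secondary outcomes, and neither primary outcome is defined by housing.

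All of this limits the point without removing it. Nothing in the plan separates the two periods, and the planned model can give the wrong 12-month answer.

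**Conclusion.** The concern holds in a limited form. The plan states a one-year housing hypothesis but tests housing only through a growth model in which two of four follow-up visits fall, nominally, in the rent-paid period. If nothing is retained, a linear model with free intercepts implies 0.2e at 12 months: 4 to 16 points for e between 20 and 80. A common intercept gives 0.4e under equal weighting, 8 to 32 points, and this figure is less certain. The sign of the slope difference turns on how the intercept is handled, which the plan does not settle for this outcome.

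The result rests on a linear shape, no baseline difference, paid nights counting as housed, and an abrupt loss of the whole difference when rent stops. That last assumption was chosen to show the problem; it is not a prediction. The point is worth correcting because the change is cheap, but it does not touch the primary outcomes.

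**What to change.** Amend Study Aim 1 of the SAP as follows.

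1. Define a housed day on Form 90 and state whether project-paid nights count.
2. Prespecify that the one-year housing claim rests on the between-arm contrast in % days housed in the window before the 12-month visit, in all randomised youth, adjusted for baseline. A piecewise growth model with a knot at 6 months is an alternative, provided that the level may drop there; two joined lines are not enough.
3. Report the rent-support period separately, and not as evidence of retained housing.
4. If late move-in puts paid nights in the 12-month window, keep them as housed in the main contrast and show a sensitivity analysis without them.

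The cost is SAP wording, plus rent-payment dates for item 4. The documents do not say that these dates are recorded, but a project that pays the rent should have them. No new visits or participants are needed. The contrast draws on fewer visits and so is less precise, and the reported housing effect will probably be smaller.
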